- The painless shock impedance was used as a surrogate parameter for the integrity of the DF4 connector system. No shift of the painless shock impedance greater than 20Ω was reported between 3- and 6-month follow-up in 150 evaluable patients. A confidence interval of the shift rate was calculated to [0.000, 0.024]. The endpoint was met.
- The RV pacing thresholds of the DF4 and DF-1 systems were compared. A non-inferiority test with a non-inferiority limit of 0.2 V was applied. The Wilcoxon test delivered a p-value of <0.001. The endpoint was met.

Secondary endpoints

- Due to the new right atrial threshold monitoring feature in the Ilesto family, the manual and the triggered automatic atrial threshold measurements were compared. Equality was shown within the specified range of [-0.2V, 0.2V]. The endpoint was met.
- The right ventricular sensing of the DF4 ICD leads was investigated at the 3-month follow-up. The rate of appropriate sensing was calculated to 99.35% (95%-CI: [0.965, 1.000]). The rate is statistically significant higher than 93%. The endpoint was met.
- The right ventricular pacing of the DF4 ICD leads was investigated at the 3-month follow-up. The rate of appropriate pacing was calculated to 100% (95%-CI: [0.977, 1.000]). The rate is statistically significant higher than 93%. The endpoint was met.
- The conversion of ventricular tachycardia and fibrillation of induced and spontaneous episodes were investigated in the patients with DF4 devices. 156 patients experienced an induced or spontaneous VT or VF. In all cases the fast ventricular rhythm was converted successfully to sinus or paced rhythm. The success rate of VT/VF conversion was 100% (95%-CI: [0.977, 1.000]). The endpoint was met.
- One SADE related to the DF-1 ICD family was reported, resulting in an SADE rate of 1.52 % (95%-CI: [0.000, 0.082]). It was concluded that the SADE rate for the DF-1 ICD family is statistically significant lower than 10%. The endpoint was met.
- 2 SADEs related to the right ventricular ICD DF-1 lead occurred in 66 patients from implantation to 3-month follow-up. This results in a SADE rate of 3.03% (95%-CI: [0.004, 0.105]). The upper confidence interval exceeds the defined limit of 0.1 - but statistical significance was not expected due to the low sample size of the DF-1 devices.

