8.1.4.16 Tachyarrhythmia episodes

During the course of the study the following tachyarrhythmia episodes have to be recorded, analyzed and evaluated on the tachyarrhythmia episode form:

- All episodes detected in the VT-1, VT-2 or VF-zone
- All episodes with attempted and/or delivered therapies (ATP and/or shock)
- The first new and last two AF and/or SVT episodes between two follow-ups.

The appropriateness of the episode detection and the success of the delivered ATPs and/or shocks to terminate the episode will be evaluated. The corresponding IEGM should be stored by opening it manually and provided to the sponsor (see section 8.1.4.19). In case of new onset of AF, the investigator will be asked if the episode was detected by Home Monitoring prior to the follow-up.

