9.3 Implantation

The implantation can only be performed after enrollment of the patient. The implantation procedure will follow the clinical routine, and the instructions for use for the investigational product have to be adhered to. Please refer to section 8.1.4.3 for further details.

All patients will be implanted with one of the Acticor 7 or Rivacor 7/5 devices and patients with VR-T DX devices will additionally be implanted with a Plexa S DX with DF4 connector (65/15, 65/17).

Patients with planned upgrade from pacemaker or ICD to ICD or CRT-D or device exchange may also be included in the study.

1. Perform lead measurements via pacing sensing analyzer (any analyzer can be used but BIOTRONIK device recommended; no documentation in eCRF required)
2. Perform device-based measurements of pacing thresholds and sensing amplitudes, pacing impedances and shock impedances via Renamic programmer (see 8.1.4.15)
3. Evaluate system performance (sensing and pacing)
4. Document and evaluate tachyarrhythmia episodes, if applicable (e.g. if defibrillation threshold test was performed) (see 8.1.4.16)
5. Optional at implantation: Perform Automatic LV VectorOpt Test (see 8.1.4.8)
6. Program the following mandatory device settings:
 - Home Monitoring 'ON'
 - For CRT-D patients implanted with Acticor 7 or Rivacor 7 devices (with exception of patients with chronic complete AV block), optional at implantation: CRT AutoAdapt 'ON'
 - Recording episode IEGMs (event-triggered) 'ON'
7. Document current medication on the medication log (see 8.1.4.21)
8. For HF-T QP patients: Document MPP settings, if applicable (see 8.1.4.12)
9. Assess the ICD/CRT-D design (see 8.1.4.5)
10. Assess the of Plexa S DX lead handling, if applicable (see 8.1.4.6)
11. Assess the Selectra catheter handling, if applicable (see 8.1.4.7)
12. Register to Home Monitoring Service Center (optional at implantation)
13. Complete the electronic Case Report Form (eCRF) in a timely manner
14. Provide programmer data (see 8.1.4.19)
15. Report all adverse events. In case of a serious adverse event, or adverse device effect (ADE), please provide the information immediately to BIOTRONIK, and inform the ethical committee, if required. Report adverse events within the indicated timelines (see section 18.9).

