		DXSHKAS01	Shock(s) successfully terminated the episode in VF zone	nominal	 Yes  No
		CEEPOUT01	Episode outcome in VF zone	nominal	 Spontaneously self-terminated  Successful external defibrillation  Patient death  Other
		COEPOUT01	Specification episode outcome in VF zone	text	n.a.

Therapy in VT zone

Data file CEEPNUM	Notes	Variable name	Variable label	Variable level	Nominal values
tachy- arrhythmia_ episode	No report	DX1THAT02	First therapy delivered in VT zone	nominal	 ATP  Shock  No therapy (shock charging aborted)
		DXATPTOT02	Number of ATP attempts in VT zone	nominal	 n.a.
		DXATPRES02	ATP results in VT zone	nominal	 Episode terminated by ATP  Shock(s) delivered after ATP failure  No shock delivered after ATP failure
		DXSHKTOT02	Number of shocks delivered in VT zone	ordinal	n.a.
		DXSHKAS02	Shock(s) successfully terminated the episode in VT zone	nominal	 Yes  No
		CEEPOUT02	Episode outcome in VT zone	nominal	 Spontaneously self-terminated  Successful external defibrillation  Patient death  Other
		COEPOUT02	Specification episode outcome in VT zone	text	n.a.

Appropriateness of episode detection per episode

Appropriateness of episode detection will be evaluated with respect to the consequences the detection has on the delivery of an ICD therapy.

- Detection zones that (may) result in delivery of a therapy (depending on the programming): VT1/VT2 or VF
- Detection zone that will never result in the delivery of a therapy: nsVT/nsT, ATR, or SVT
- Rhythm (episode assessment) that requires a therapy: sustained VT/VF and non-sustained VT/VF (with successful therapy; see below)
- Rhythm (episode assessment) that does not require a therapy: The remaining options for episode assessment and non-sustained VT/VF (without successful therapy, see below)

[figure not shown]

	Rhythm that requires a therapy	Rhythm that does not require a therapy

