Detection zone that (may) result in delivery of a therapy (depending on the programming)	Appropriate detection of ventricular arrhythmia (true positive)	Inappropriate detection (non-ventricular arrhythmia falsely detected; false positive)
Detection zone that will never result in the delivery of a therapy	Inappropriate detection (ventricular arrhythmia not detected; false negative)	Appropriate detection (non-ventricular arrhythmia correctly detected; true negative)

Data file patient_ display_id_full	Notes	Variable name	Variable label	Variable level	Nominal values
tachy- arrhythmia_ episode_SAR	descriptive; case listings for all fn and fp episodes	tp_episode_detection_SAR ³³	Appropriate detection of ventricular arrhythmia (true positive)	nominal	 1  0
		fn_episode_detection_SAR ³⁴	Inappropriate detection (ventricular arrhythmia not detected; false negative)	nominal	 1  0
		tn_episode_detection_SAR ³⁵	Appropriate detection (non-ventricular arrhythmia correctly detected; true negative)	nominal	 1  0
		fp_episode_detection_SAR ³⁶	Inappropriate detection (non-ventricular arrhythmia falsely detected; false positive)	nominal	 1  0

The episode detection is evaluated by the following values:

- Sensitivity = sum tp / (sum tp + sum fn)
- Specificity = sum tn / (sum tn + sum fp)
- PPV = sum tp / (sum tp + sum fp)
- NPV = sum tn / (sum tn + sum fn)

Appropriateness of episode detection per patient

Data file patient_ display_id_full	Notes	Variable name	Variable label	Variable level	Nominal values
data_SAR	descri ptive	any_tachy_detection_SAR ³⁷	Any tachy-arrhythmia episode with non-missing information about the detection zone	nominal	 Yes  No
		any_tachy_detection_VTVF_SAR ³⁸	Any tachy-arrhythmia episode with detection in the VT1/VT2 or VF zone	nominal	 Yes  No
		only_tachy_app_detection_SAR ³⁹	All tachy-arrhythmia episodes with appropriate detection (all true positive or true negative)	nominal	 Yes  No
		any_tachy_inapp_detection_SAR ⁴⁰	Any tachy-arrhythmia episode with inappropriate detection (any false positive or false negative)	nominal	 Yes  No

ATP efficacy per tp episode

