		only_tpVT_ATP_success_SAR ⁵⁴	All true positive VT episodes with ATP therapy were successful	nominal	 Yes  No
		any_tpVT_ATP_nosuccess_SAR ⁵⁵	Any true positive VT episode with delivered but not successful ATP therapy	nominal	 Yes  No

Shock efficacy per tp episode

Only applicable for true positive tachy-arrhythmia episodes⁵⁶ as defined before.

Data file patient_ display_id_full	Notes	Variable name	Variable label	Variable level	Nominal values
tachy- arrhythmia_ episode_SAR	descri ptive	tpVF_shock_SAR ⁵⁷	True positive episode in VF zone with at least one shock therapy	nominal	 1  0
		tpVF_shock_success_SAR ⁵⁸	True positive episode in VF zone with successful shock therapy	nominal	 1  0
		n_shock_tpVF_SAR ⁵⁹	Number of shocks per true positive episode in VF zone	Metric reported as nominal	 1  2 ...
		tpVT_shock_SAR ⁶⁰	True positive episode in VT zone with at least one shock therapy	nominal	 1  0
		tpVT_shock_success_SAR ⁶¹	True positive episode in VT zone with successful shock therapy	nominal	 1  0
		n_shock_tpVT_SAR ⁶²	Number of shocks per true positive episode in VT zone	Metric reported as nominal	 1  2 ...

The shock efficacy is evaluated by the following values:

- Shock VF efficacy rate = $\text{sum}\{\text{tpVF_shock_success_SAR}\} / \text{sum}\{\text{tpVF_shock_SAR}\}$
- Shock VT efficacy rate = $\text{sum}\{\text{tpVT_shock_success_SAR}\} / \text{sum}\{\text{tpVT_shock_SAR}\}$

Shock efficacy per patient (for tp episodes)

Only applicable for patients with any true positive tachy-arrhythmia episodes⁶³ as defined before.

Data file patient_ display_id_full	Notes	Variable name	Variable label	Variable level	Nominal values
data_SAR	descri ptive	any_tpVF_shock_SAR ⁶⁴	Any true positive VF episode with shock therapy	nominal	 Yes  No
		only_tpVF_noshock_SAR ⁶⁵	All true positive VF episodes without shock therapy	nominal	 Yes  No
		only_tpVF_shock_success_SAR ⁶⁶	All true positives VF episodes with shock therapy were successful	nominal	 Yes  No

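### SAP 8.2.6 does not visibly separate episodes induced at defibrillation testing from spontaneous ones, so sensitivity, PPV and the ATP and shock efficacy rates can be raised by an unknown amount

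*SAP*

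**What the plan says.** Protocol 9.3 (Implantation), step 4, instructs the site: "Document and evaluate tachyarrhythmia episodes, if applicable (e.g. if defibrillation threshold test was performed) (see 8.1.4.16". Defibrillation testing is thus the protocol's own example of a reason to record an episode at implantation, and the cross-reference leads to the general rule for tachyarrhythmia episodes.

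That rule, Protocol 8.1.4.16, puts on one form "All episodes detected in the VT-1, VT-2 or VF-zone" and "All episodes with attempted and/or delivered therapies (ATP and/or shock". It does not limit recording to spontaneous episodes.

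SAP 8.2.6 lists its inputs from that form: episode number, detection zone, episode assessment, first therapy, ATP and shock counts and results, and outcome. None marks an episode as induced, and no episode date or visit is listed. Sensitivity and PPV are sums over all classified episodes. Shock efficacy in the VF zone divides episodes counted as "True positive episode in VF zone with successful shock therapy" by true positive episodes with at least one shock. Success comes from one yes/no item per episode, "Shock(s) successfully terminated the episode in VF zone". The number of shocks is tabulated separately and does not enter the rate.

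SAP 5.6 foresees no repetition of analyses in subsets, and SAP 8.6 states no hypothesis for this chapter.

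**The concern.** An arrhythmia provoked under controlled conditions and a clinical event in daily life are different tests of a defibrillator. If both enter one numerator and one denominator, the rate is a weighted average, and the weights are set by how often sites choose to test. Testing is optional here, so two sites with identical device performance in spontaneous arrhythmias could report different rates.

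Protocol 7.1 includes the performance and efficacy of the Cor Family among its aims, and Protocol 4.7.1 describes a new electro-mechanical platform. The rates in SAP 8.2.6 are where detection and therapy performance will be read. A reader of the report would naturally take them as performance in clinical use.

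**Working it through.** **The nearest figure in the documents.** The plan gives no expected detection or shock efficacy rate. Protocol 5.2.1 reports for the DF4 study that "156 patients experienced an induced or spontaneous VT or VF", all converted, with an exact 95% interval of [0.977, 1.000]. Check: with no failures in n, the lower bound is 0.025^(1/n); for n = 156 it is 0.9766, which agrees. The 156 are 156/173 = 90.2% of the DF4 patients. They are patients rather than episodes, and the protocol does not say how many were induced. The figure shows that the sponsor has pooled the two kinds before. It does not give the induced share.

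**Which rates are affected.** With tp, fp, tn and fn as defined in SAP 8.2.6:

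- Sensitivity = tp/(tp + fn) and PPV = tp/(tp + fp): both rise when induced true positives are added.
- Shock and ATP efficacy = successes/treated true positives: these rise if induced episodes succeed more often than spontaneous ones. For ATP this applies only where ATP was delivered in an induced episode.
- Specificity = tn/(tn + fp) and NPV = tn/(tn + fn): no tp term, so not raised this way.

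**Size under assumptions.** Let I be the number of induced episodes, all successful, S the number of spontaneous episodes and s their success rate. The pooled rate is (I + s·S)/(I + S).

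Assumed inputs:

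- I = one induced episode per tested patient, with the tested share of the planned 127 patients varied.
- S = 12. This is an order of magnitude only. In the Ilivia/Plexa study (Protocol 5.2.2) ATP one-shot was attempted in 5 of 111 group A patients, assessed at 6 months; 5/111 × 127 × 2 = 11.4 for 12 months. That counts patients with one kind of therapy, not all shocked episodes.
- s = 80%, so 9.6 expected successes and 2.4 expected failures.

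| Share tested | I | Pooled rate | Induced share of denominator |
|---|---|---|---|
| 0% | 0 | 9.6/12 = 80.0% | 0% |
| 10% | 13 | 22.6/25 = 90.4% | 52% |
| 30% | 38 | 47.6/50 = 95.2% | 76% |
| 50% | 64 | 73.6/76 = 96.8% | 84% |
| 80% | 102 | 111.6/114 = 97.9% | 89% |

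The 2.4 expected failures stay the same in every row; only the denominator grows.

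**Sensitivity of the result.** At 30% tested, S = 6 gives (38 + 4.8)/44 = 97.3% and S = 25 gives (38 + 20)/63 = 92.1%. With S = 12 and s = 90%, the range from 10% to 80% tested is 23.8/25 = 95.2% to 112.8/114 = 98.9%.

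**The case against.** The footnotes that derive the SAP 8.2.6 variables cannot be read, a figure after the detection rules is missing, and the eCRF is not available. A restriction to spontaneous episodes could sit there. This stands as a limit. It is weakened by SAP 1.3, under which the variable tables also carry items used only for derivation: no induced/spontaneous item appears among them.

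A reader might infer that the pooled rates would hide any detection or shock weakness of the new platform. The documents do not support that:

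- SAP 8.2.6 requires case listings of every false negative and false positive episode.
- It tabulates the number of shocks per true positive episode in each zone. If success is close to 100%, the share of episodes with one shock is nearly the first-shock success rate.
- It reports patients with any true positive episode in which shock therapy did not succeed.

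Nor is the DF4 result an example of masking. A pooled 100% leaves no failure to hide.

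It is also fair to say that testing is optional and may be rare. Protocol 8.1.4.16 asks whether delivered therapy ended the episode, and the yes/no item answers that. First-shock success is therefore an addition, not a repair. Finally, these are further data of interest under Protocol 7.5.1, with no hypothesis and no bearing on pass or fail.

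What remains is narrower: the headline rates mix two kinds of episode in a proportion that the plan neither fixes nor reports.

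**Conclusion.** The point holds in limited form. On the visible text, induced and spontaneous episodes share one form and one set of formulas, so sensitivity, PPV and the ATP and shock efficacy rates can be raised by induced episodes.

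The actual size is unknown, because the documents give neither the testing frequency nor the number of spontaneous episodes. The range of about 90% to 98% against a true 80% is an illustration. It rests on 12 spontaneous episodes, complete success in induced ones, and 10% to 80% of 127 patients tested. With few tests the effect is small. It would be wrong to conclude that the rates will be near 100% because of induced episodes; the documents show only that they could be.

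This is a reporting weakness in a descriptive analysis. It should be corrected, but it does not threaten the study's conclusion on its primary hypothesis.

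**What to change.** In SAP 8.2.6, classify every episode as induced or spontaneous. Use an existing eCRF item if there is one, otherwise add one, or classify as induced any episode arising at the implantation or testing procedure. The last route needs the episode date or visit, which is not among the inputs now listed. State the rule in the body of the SAP. Then report sensitivity, PPV and the ATP and shock efficacy rates separately for the two classes, with numerators and denominators and with spontaneous as the main figure.

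Optionally, cross-tabulate shock success by the number of shocks already collected (`DXSHKTOT01`, `DXSHKTOT02`), so that success with one shock can be read directly.

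The cost is one flag and split tables. The spontaneous rates will rest on few episodes and may look less favourable. Even with no failure, the exact lower 95% bound, 0.025^(1/n), is 69.2% for 10 episodes and 83.2% for 20, before any allowance for several episodes in one patient. Nothing in the primary analysis changes.

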3 INTRODUCTION

Sudden cardiac death (SCD) is the most common cause of death in western industrialized countries. SCD affects e.g. about 156,000 people in Germany and it adds up to about 15 - 20% of all natural deaths¹⁻³.

Implantable cardioverter defibrillators (ICD) are a common therapy approach to improve the survival of patients at risk of sudden cardiac death⁴ by the termination of life-threatening ventricular tachyarrhythmias (VTA).

Antitachycardia pacing in the ventricular fibrillation zone

ICDs terminate VTAs by administration of antitachycardiac pacing (ATP) or high-energy electric shocks. While ATP has a lower conversion rate than shocks, they are not painful. In slower VTAs, which are not immediately life-threatening, several attempts of ATP are typically started before a shock is delivered in case of failure of all ATP attempts. In contrast, for fast VTAs detected in the "ventricular fibrillation" (VF) zone, only one attempt of ATP will be delivered prior to shock delivery, to avoid protracted repeated ATP attempts in this urgent situation.

Atrial sensing

The choice of single vs. dual chamber ICDs varies per country, with a majority of countries (60%) having a preference for single chamber ICDs⁵.

In patients implanted with single chamber ICDs, no information about the atrial rhythm is available. Early information about clinical events such as the onset of atrial fibrillation may allow faster medical treatment, which can improve the clinical status of the patients^{6,7}. Furthermore, inappropriate shocks frequently result from supraventricular tachyarrhythmias such as sinus tachycardia, atrial fibrillation or atrial flutter⁸⁻¹⁰, which are difficult to identify in single-chamber devices without atrial sensing. Inappropriate shocks occur significantly more often in patients with single chamber than dual chamber ICDs (24% vs. 8%; p<0.02)⁸. The DATAS study could show that implantation of a dual chamber ICD in patients with a conventional single chamber ICD indication, was associated with less clinically significant adverse events^{11,12}. The BIOTRONIK DX system allows monitoring of the atrial rhythm in a single chamber ICD and thus potentially allows reduction of inappropriate shocks and fast reaction to atrial fibrillation.

Dual chamber devices are indicated for patients with abnormal sinus node function, atrial arrhythmias, bradycardia, or second/third degree atrio-ventricular block¹³.

Cardiac Resynchronization Therapy (CRT)

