18.5.1 Definition of endpoint-related SADEs

The SADE-free rate calculated for the primary endpoint will be based on the total number of subjects with at least one SADE related to a Cor Family ICD until 3-month follow-up. SADEs that occur later than the 3-month follow-up, and SADEs with onset date later than or exactly at 123 days after implantation in case the 3-month follow-up was not conducted or conducted outside the specified time interval do not contribute to this endpoint.

However, SADEs until the 12-month follow-up will contribute to secondary endpoint 1.

Endpoint-related SADEs are complications, which are device-related adverse events that are corrected using invasive measures or require invasive measures to correct or which result in the loss of significant device function. Device-related adverse events, which are corrected by non-invasive measures (e.g. reprogramming) are considered observations and will not contribute to the primary endpoints.

Only SADEs directly related to the device (SADE-d) will be included in the endpoint. SADEs which are securely related to the implantation procedure (SADE-p) (e.g. pocket infection, etc.) will not be considered for the primary endpoint. Inappropriate ICD therapies which are not related to a device defect (e.g. if the device function is according to device specification) will also not be considered for primary endpoint analysis. Furthermore 'Twiddler's' syndrome will not be considered for the endpoint analysis. If any amply documented external physical influence (e.g. accident, sport, twiddling) or medical AE caused the SADE, it does not contribute to this endpoint.

All serious adverse device effects that meet these primary endpoint criteria (confirmed by an internal endpoint committee) for the Cor Family ICDs will be included in the primary endpoint event analysis. Adverse events with a device relation of "not related" will not contribute to or be included in the evaluation of the primary safety endpoint.

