5.1 Descriptive analyses

CIP chapter 11.1 Statistical design, method and analytical procedures

... For continuous variables descriptive statistics (mean, standard deviation, median, minimum, maximum and quartiles) will be calculated. For nominal variables absolute and relative frequencies will be calculated based on non-missing data. Ordinal variables are described similarly as continuous data (minimum, 1. quartile, median, 3. quartile, and maximum) or by absolute and relative frequencies based on non-missing data of each category.

For illustration, see the following standard tables with and without subgroup analyses based on dummy data.

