8.1 Analysis set

The following analyses are performed for the investigational device analysis set²² and separately for the Plexa analysis set²³.

- Baseline characteristics and medical history
- Lead measurements
- Sensing and pacing assessment
- Adverse Events
- Device Deficiencies

The following analyses are performed for the Cor family analysis set²⁴

- Assessment of ICD/CRT-D design
- Arrhythmias and their treatment by the ICD/CRT-D system
- Usage of QuickCheck
- Assessment of statistic for ATP optimization
- RV/LV active capture control at permanent DDI mode

The following analyses are performed for the AV Opt analysis set²⁵

- AV delay optimization feature

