		any_tpVF_shock_nosuccess_SAR ⁶⁷	Any true positive VF episode with not successful shock therapy	nominal	 Yes  No
		any_tpVF_shock_SAR ⁶⁸	Any true positive VT episode with shock therapy	nominal	 Yes  No
		only_tpVF_noshock_SAR ⁶⁹	All true positive VT episodes without shock therapy	nominal	 Yes  No
		only_tpVF_shock_success_SAR ⁷⁰	All true positive VT episodes with shock therapy were successful	nominal	 Yes  No
		any_tpVF_shock_nosuccess_SAR ⁷¹	Any true positive VT episode with not successful shock therapy	nominal	 Yes  No

Therapy efficacy per patient (for tp episodes)Only applicable for patients with any true positive tachy-arrhythmia episodes⁷² as defined before.

Data file patient_ display_id_full	Notes	Variable name	Variable label	Variable level	Nominal values
data_SAR	descri ptive	any_tpVF_therapy_SAR ⁷³	Any true positive VF episode with ATP or shock therapy	nominal	 Yes  No
		only_tpVF_therapy_success_SAR ⁷⁴	All true positive VF episodes with ATP or shock therapy were successful	nominal	 Yes  No
		any_tpVF_therapy_nosuccess_SAR ⁷⁵	Any true positive VF episode with not successful shock or ATP therapy	nominal	 Yes  No
data_SAR	descri ptive	any_tpVT_therapy_SAR ⁷⁶	Any true positive VT episode with ATP or shock therapy	nominal	 Yes  No
		only_tpVT_therapy_success_SAR ⁷⁷	All true positive VT episodes with ATP and shock therapy were successful	nominal	 Yes  No
		any_tpVT_therapy_nosuccess_SAR ⁷⁸	Any true positive VT episode with not successful ATP or shock therapy	nominal	 Yes  No

Inappropriate therapies per fp episode

Only applicable for false positive tachy-arrhythmia episodes⁷⁹ as defined before.

Data file patient_display_id_full	Notes	Variable name	Variable label	Variable level	Nominal values
tachy- arrhythmia_ episode_SAR	descri ptive	fp_episode_ATP_SAR ⁸⁰	False positive episode with inappropriate ATP or ATP one-shot therapy	nominal	 1  0

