		fp_episode_shock_SAR ⁸¹	False positive episode with inappropriate shock therapy	nominal	 1  0
		fp_episode_ATP_shock_SAR ⁸²	False positive episode with inappropriate ATP, ATP-one-shot, or shock therapy	nominal	 1  0

Data file patient_display_id_full	Notes	Variable name	Variable label	Variable level	Nominal values
tachy- arrhythmia_ episode_SAR	descri ptive or case listing	n_ATP_fp_episode_SAR ⁸³	Number of inappropriate ATPs (ATP one-shot counts as 1) per false positive episode	Metric reported as nominal	 1  2  ...
		n_shock_fp_episode_SAR ⁸⁴	Number of inappropriate shocks per false positive episode	Metric reported as nominal	 1  2  ...
		n_ATP_shock_fp_episode_SAR ⁸⁵	Number of inappropriate ATPs (ATP one-shot counts as 1) or shocks per false positive episode	Metric reported as nominal	 1  2 ...

Inappropriate therapies per patient (for fp episodes)

Only applicable for patients with any false positive tachy-arrhythmia episodes⁸⁶ as defined before.

Data file patient_ display_id_full	Notes	Variable name	Variable label	Variable level	Nominal values
data_SAR	descri ptive	any_fp_ATP_therapy_SAR ⁸⁷	Any false positive episode with inappropriate ATP therapy	nominal	 Yes  No
		any_fp_shock_therapy_SAR ⁸⁸	Any false positive episode with inappropriate ATP or shock therapy	nominal	 Yes  No
		any_fp_ATP_shock_therapy_SAR ⁸⁹	Any false positive VF episode with inappropriate ATP or shock therapy	nominal	 Yes  No

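### SAP 8.2.6: the four per-patient VT shock variables reuse the VF names, two of three inappropriate-therapy labels contradict their variables, and no all-patient incidence of inappropriate therapy is printed

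*SAP*

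**What the plan says.** SAP 8.1 lists arrhythmias and their treatment under the sentence "The following analyses are performed for the Cor family analysis set". SAP 7.3 defines that set by implantation attempt.

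Within SAP 8.2.6:

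- The per-patient shock-efficacy table has four VF rows (footnotes 64 to 67) and four VT rows (footnotes 68 to 71), all in `data_SAR`. The first VT row is labelled "Any true positive VT episode with shock therapy", yet its variable is `any_tpVF_shock_SAR`.
- The per-patient table of inappropriate therapies has three rows (footnotes 87 to 89) and opens with a restriction: "Only applicable for patients with any false positive tachy-arrhythmia episodes". Its third row, `any_fp_ATP_shock_therapy_SAR`, is labelled "Any false positive VF episode with inappropriate ATP or shock therapy".
- The only per-patient row on inappropriate behaviour outside that restriction concerns detection, not therapy: "Any tachy-arrhythmia episode with inappropriate detection (any false positive or false negative".

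SAP 5.1 sets the percentage base: "For nominal variables absolute and relative frequencies will be calculated based on non-missing data".

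On the protocol side, section 18.5.1 keeps "Inappropriate ICD therapies which are not related to a device defect" out of the primary endpoint. Section 6.2.3 names inadequate shocks as a risk of VR-T DX systems, and section 7.4 says that the risks in section 6.2 will be assessed. Table 6 in section 18.7 places inappropriate ICD therapy or shock in the band of 1 to 10 patients out of 100.

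**The concern.** SAP 1.3 describes data files with one row per unique identifier, so two patient-level variables cannot share a name in `data_SAR`. A programmer who follows the table literally would create each shock variable twice, and the second derivation would replace the first. The VF and VT per-patient shock results would then show the same data under different labels.

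Under SAP 1.3, labels come from the data management system unless the SAP defines a new one. Derived variables have no such source, so the SAP's label is what the report would print. With the labels as they stand, a reader of the report would find no row for inappropriate shocks per patient, and would take the combined row to be limited to the VF zone.

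The percentage base adds a smaller difficulty. It answers how often a patient with a false detection was treated. It does not answer how many patients in the cohort received inappropriate therapy, which is the form in which Table 6 states the anticipated risk.

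**Working it through.** The plan gives no figure to reproduce here. The check compares names and labels, followed by arithmetic on the two possible denominators.

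**1. Names in the per-patient shock table**

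| VF rows (footnotes 64 to 67) | VT rows as printed (footnotes 68 to 71) |
|---|---|
| `any_tpVF_shock_SAR` | `any_tpVF_shock_SAR` |
| `only_tpVF_noshock_SAR` | `only_tpVF_noshock_SAR` |
| `only_tpVF_shock_success_SAR` | `only_tpVF_shock_success_SAR` |
| `any_tpVF_shock_nosuccess_SAR` | `any_tpVF_shock_nosuccess_SAR` |

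All four pairs are identical, which leaves 4 distinct names for 8 variables. The per-patient ATP table, the per-episode shock table and the per-patient combined-therapy table all give their VT rows separate `tpVT` names, so the intended pattern is clear.

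**2. Labels in the per-patient inappropriate-therapy table**

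| Variable | What the label covers | Agrees with the name? |
|---|---|---|
| `any_fp_ATP_therapy_SAR` | ATP | yes |
| `any_fp_shock_therapy_SAR` | ATP or shock | no |
| `any_fp_ATP_shock_therapy_SAR` | ATP or shock, VF episodes only | no |

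The episode-level table just above (footnotes 80 to 82) confirms the names rather than the labels. There, `fp_episode_shock_SAR` is shock only, and `fp_episode_ATP_shock_SAR` covers ATP, ATP one-shot or shock without a VF limit. So 2 of 3 labels are wrong.

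**3. Denominator**

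Let k be the number of patients with inappropriate therapy, F the number with any false-positive episode, and N the size of the analysis set.

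- Printed percentage = 100 × k / F
- Cohort percentage = 100 × k / N
- Ratio of the two = N / F

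The documents give no expected F or k, so both are assumed. N = 127 is the planned enrolment (Protocol 8.2.4), used as a stand-in for the Cor Family set.

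| k | F | Printed | Cohort (N = 127) | Ratio |
|---|---|---|---|---|
| 3 | 5 | 60% | 2.4% | 25.4 |
| 3 | 10 | 30% | 2.4% | 12.7 |
| 3 | 20 | 15% | 2.4% | 6.35 |
| 7 | 10 | 70% | 5.5% | 12.7 |
| 14 | 20 | 70% | 11.0% | 6.35 |

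The first three lines show one cohort rate printed as three different percentages. The last two show one printed percentage standing for two cohort rates, one inside the Table 6 band of 1 to 10 out of 100 and one above it.

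**The case against.** Much can be said for the plan as it stands.

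- **The denominator is a stated choice.** It mirrors the true-positive restriction on the ATP, shock and combined-therapy tables. Under the SAP's definitions inappropriate therapy arises only in false-positive episodes, so the numerator is complete. The standard table in SAP 5.1.1 prints the absolute count, SAP 7.9.1 reports the Cor Family set size, and SAP 8.2.6 requires case listings of all false-positive and false-negative episodes. A reader might infer that the cohort rate is lost or miscalculated; it is not, since one division gives it. This argument stands, with one qualification: for shocks the reader must first know which row is shock only, and the labels obscure that.
- **Overwriting is not established.** A reader might infer that the VF and VT results will come out identical. The VF and VT rows have separate footnotes and correct VF and VT labels, and the footnote texts are not visible. The derivations may be right. This stands: the visible fault lies in the names.
- **This is not the only reporting route.** A reader might infer that inappropriate therapies would otherwise go unreported. Protocol 18.5.1 removes those without a device defect from the primary endpoint, not from adverse event reporting, and SAP 8.2.11 takes adverse events from the Vigilance report. What can be said is that SAP 8.2.6 holds the SAP's only patient-level table of them.
- **The literature contrast is not a planned benchmark.** The Introduction says "Inappropriate shocks occur significantly more often in patients with single chamber than dual chamber ICDs (24% vs. 8%; p<0.02". That is background on a cited study. Protocol 8.2.2 states that there is no comparator, and the cited study's definitions and follow-up are not available here.
- **Not every table is affected.** The per-patient ATP and combined-therapy tables have correct, separate names.

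**Conclusion.** The point holds as a drafting correction with a modest reporting gap. Four VT variable names duplicate VF names, and two of three labels in the inappropriate-therapy table contradict their variables. As a result, no row is correctly labelled as inappropriate shocks per patient. The percentages in that table are conditional on a false-positive episode, and the SAP prints no patient-level incidence to set beside Table 6.

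Loss of the VF or VT shock data follows only if the variables are coded literally from the table. The gap between conditional and cohort percentages (a factor of 6.35 to 25.4 in the illustration) rests on assumed counts of 20 to 5 patients with false-positive episodes out of 127.

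Severity is minor. Protocol 7.5.1 lists these as further data of interest, SAP 5.3 treats everything beyond the primary endpoint as exploratory, and SAP 8.6 sets no hypotheses for this chapter. The primary endpoint, its test and the sample size are unaffected. It is still worth correcting before programming, because SAP 1.2 requires quality control only for endpoint analyses, so a slip in these tables may not be caught.

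**What to change.** In SAP 8.2.6:

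1. Rename the VT rows at footnotes 68 to 71 as `any_tpVT_shock_SAR`, `only_tpVT_noshock_SAR`, `only_tpVT_shock_success_SAR` and `any_tpVT_shock_nosuccess_SAR`, and check that their derivation footnotes refer to VT episodes.
2. Relabel `any_fp_shock_therapy_SAR` so that it names inappropriate shock only. Relabel `any_fp_ATP_shock_therapy_SAR` so that it names inappropriate ATP or shock in any false-positive episode, without the VF limit.
3. Keep the conditional table. Beside it, report the same three rows with the whole Cor Family analysis set (implantation attempts) as denominator. An exact 95% confidence interval is optional.
4. While editing, align the ATP efficacy formulas, which use `VFtp_` and `VTtp_` prefixes, with the variables defined as `tpVF_` and `tpVT_`.

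The cost is SAP wording and a few lines of code. No new data are needed.
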